9.3. Procedures for Monitoring Subject Compliance

Subject compliance for investigational product administration is not an issue because the study materials will be administered by study staff. Subjects will be reminded to return to the clinic for the Day 8 follow-up. In addition, attempts to reschedule missed appointments, within allowable day ranges, will be made.

10. PHARMACOKINETIC SAMPLE COLLECTION

Blood samples (approximately 10 mL each draw) will be obtained for PK assessments within 2 hours prior to dosing and at 2, 5, 10, 15, 20, and 30 minutes and 1, 2, 4, 8, 12, 24, 36, and 48 hours post dose. These sampling points should allow for adequate and full characterization of the Scopolamine HBT PK profile.

Scopolamine HBT PK assessments will include determination of the following parameters: observed C_{max} and T_{max} , V_d/F , $t_{1/2}$, Cl/F , AUC_{last} , AUC_{∞} , $C_{max}/Dose$, MRT, and $AUC_{\infty}/Dose$. Samples will be analyzed for Scopolamine HBT at Battelle in Columbus, Ohio, using a high-performance liquid chromatography-tandem mass spectrometry method validated with respect to accuracy, precision, linearity, sensitivity, and specificity. Samples will be shipped as agreed upon by the site and Battelle. It is expected that plasma samples will be analyzed and concentration time profiles constructed for each cohort to assist the DSMB in making dose-escalation recommendations. After analysis, samples will be stored until study report approval and permission from the sponsor has been received to dispose or ship the samples to a sponsor-designated location.

The backup (“B”) PK samples will be stored at the investigator site at -20°C or lower until directed to ship by Battelle. These samples will be shipped to Battelle’s Chemistry Technical Center in Columbus, Ohio, for confirmatory testing, if applicable. Approximately 2 mL of plasma for each PK assessment will be transferred to a long-term storage facility where samples will be stored at -20°C or lower for at least 2 years after FDA approval of the last indication for this product. These backup samples may be used for additional or repeat PK testing, as required.

10.1. Clinical Blood Sample Collection

Blood samples (approximately 24 mL at screening and 16 mL on subsequent days) will be obtained for clinical laboratory testing. Serum chemistry and hematology (including coagulation) tests will be performed at screening, baseline (Day-1), at 24 and 48 hours post dose, and at Day 8 (refer to Section 11.1.9.1 and Section 11.1.9.2 for specific tests). Serum pregnancy testing will be performed at screening, Day-1, and at Day 8 (refer to Section 11.1.9.4). Serology will be performed at screening only (refer to Section 11.1.9.5 for specific tests).

The total blood volume to be collected in this study is approximately 250 mL. This includes blood collection for PK assessments and clinical laboratory testing but does not include additional clinical testing deemed necessary by the investigator or designee for subject safety.

10.2. Urine Sample Collection

Urine samples will be obtained for urinalysis at screening, baseline (Day-1), at 24 and 48 hours post dose, and at Day 8 (refer to Section 11.1.9.3 for specific tests). Urine drug screening will be performed on an aliquot of the urine sample at screening, baseline (Day-1), and at Day 8 (refer to Section 11.1.8 for specific tests).

Urine will also be obtained for separation and identification of urinary Scopolamine HBT and its metabolites. For urine samples for separation and measurement of metabolites, a “clean catch” urine specimen will be collected. For each subject, the date and time of collection, as well as the estimated volume of each void, will be recorded from pre-dose through 24 hours post dose. The urine specimens will be stored in a polyethylene, screw-cap container by interval and subject and, immediately upon collection, will be stored refrigerated. The urine will be mixed well before transferring two 10-mL aliquots into 2 separate 15-mL screw-cap, polypropylene, conical-shaped vials. Refer to Section 9.1.1.3 and the PK Sample Instruction Manual for collection and processing details.

10.3. Sample Analysis

The plasma concentration time profiles for Scopolamine HBT will be subject to a model-independent PK analysis (noncompartmental analysis) using WinNonlin software by a Battelle Memorial Institute pharmacokineticist to estimate the PK parameters shown in Table 9. PK and safety ± will undergo PD analysis and evaluation.

Table 9: Pharmacokinetic Parameters

Parameter	Description
C_{\max}	Maximum measured plasma time concentration over the time span specified
T_{\max}	Time of the maximum measured plasma concentration. If the maximum value occurs at more than one time point, T_{\max} is defined as the first time point with this value.
Apparent Volume of Distribution (Vz/F)	Volume of distribution during terminal phase calculated as Dose/AUC _∞ / λ_z
$t_{\frac{1}{2}}$	Apparent first-order terminal elimination half-life will be calculated as 0.693/ k_e .
Apparent Clearance (Cl_F)	Volume of blood or plasma cleared of drug per unit time
MRT	Mean residence time calculated as AUMC/AUC
AUC _{last}	The area under the plasma concentration versus time curve, from time 0 to the last measurable concentration, as calculated by the linear trapezoidal method
AUC _∞	The area under the plasma concentration versus time curve from time 0 to infinity. AUC _∞ is calculated as the sum of AUC _{last} plus the ratio of the last measurable plasma concentration to the elimination rate constant (k_e). The elimination rate constant will be determined from the terminal linear phase of the plasma concentration time profile.

Parameter	Description
$C_{\max}/Dose$ and $AUC_{\infty}/Dose$	Dose normalization of C_{\max} and AUC_{∞} for evaluation of dose proportionality.

No value for V_d/F , Cl/F , AUC_{∞} , $t_{1/2}$, or MRT will be reported for profiles that do not exhibit a terminal log-linear phase in the concentration versus time profile.

11. SAFETY ASSESSMENT

Safety monitoring will be conducted throughout the study; therefore, safety concerns will be identified by continuous review of data by the PI, clinic staff, clinical trial monitor, research monitor, and [REDACTED].

Study Safety Management: The PI, research monitor, [REDACTED] PVG physician, and IRB will review any safety concern.

An independent DSMB is required for this study. The DSMB will be convened to review safety data and provide recommendations to the sponsor's representative. Prior to any data being provided to the DSMB, it must be reviewed and approved for release by a study biostatistician in collaboration with the [REDACTED] biostatistician. The DSMB will review cumulative study data during scheduled in-process and ad hoc reviews to evaluate safety, study conduct, and the scientific validity and integrity of the trial. After each review of study data, the DSMB will make a recommendation to the sponsor's representative. DSMB recommendations will be documented and provided in writing (via the DSMB Chair Recommendation Form) to the [REDACTED] [REDACTED]. The sponsor's representative will then decide whether to continue, modify, or suspend the study. The [REDACTED] will communicate the final decision to the investigator, who in turn will notify the IRB as appropriate. The [REDACTED] regulatory affairs scientist will communicate the final decision to the FDA, as appropriate. A description of the DSMB's roles and responsibilities, functions, reporting requirements, meeting frequency, and the study stopping/continuation criteria is included in the DSMB charter.

Research Monitor: The DoD research monitor is responsible for overseeing the safety of the research and reporting observations/findings to the IRB or a designated institutional official. The research monitor will review all unanticipated problems involving risks to subjects or others associated with the protocol and provide an independent report of the event to the IRB. The research monitor may discuss the research protocol with the investigators; shall have authority to stop a research protocol in progress, remove individual human subjects from a research protocol, and take whatever steps are necessary to protect the safety and well-being of human subjects until the IRB can assess the research monitor's report; and shall have the responsibility to promptly report his or her observations and findings to the IRB or other designated official and the [REDACTED].

In addition to the responsibilities above, the research monitor is required to review and provide an unbiased written report for all SAEs and subject deaths to the [REDACTED] within 24 hours of his or her awareness of the event. The report provided must include, at a minimum, a brief summary of the research monitor's review of the event and event outcome, relationship of the event to the investigational product, and whether the research monitor concurs with the details of the study investigator's SAE report.

The PI (or designee) will report SAEs to the DoD research monitor. Upon receipt of an SAE report (initial or follow-up), the DoD research monitor will provide the unbiased written report using the [REDACTED] Research Monitor Report Form for each assessment. The DoD Research Monitor's report may be submitted to the [REDACTED] by the Research Monitor or the PI.

Multiple follow-up reports may be necessary for a single event, depending on when additional information becomes available. The PI (or designee) will also report all events that meet extreme and non-extreme DLT criteria, unanticipated problems, and other events with the potential to impact a subject's clinical care to the research monitor. The occurrence of any DLT(s) would result in the immediate discontinuation of dosing and study enrollment, pending a review of study data by the PI, research monitor, PVG physician, the DSMB, and the sponsor.

Medical Monitor: The medical monitor's role is separate and distinct from that of the research monitor. The medical monitor is available to serve as a resource to the clinical site and may provide consultations relating to issues such as general conduct of the study, subject eligibility, or potential protocol exceptions. The medical monitor may discuss with on-site medical staff any clinical situations that arise and provide recommendations. After the first day of dosing for each cohort, the medical monitor will review safety data with the PI to determine if it is safe to proceed with dosing the remaining subjects. The medical monitor may also perform additional tasks such as reviewing safety data listings for identification of data trends.

[REDACTED] : The [REDACTED] is responsible for the review of safety data regarding The Surgeon General, Department of the Army (TSG-DA)-sponsored products. The [REDACTED] reviews all safety events and follows them until resolution.

[REDACTED] **PVG Physician:** The [REDACTED] PVG physician, as delegated by the sponsor, evaluates all safety cases and provides the final determination on relatedness and expectedness to the product, and whether expedited reporting is warranted per current FDA regulation and guidance.

11.1. Specification of Safety Assessments

PK samples should be collected as close to the actual time point as possible (within the windows specified in [Table 8](#)); however, when multiple tests are scheduled at the same time, ECG and vital signs will be performed within 5 minutes prior to the nominal time point, and injection site and AE assessments will be performed immediately after the PK blood draw.

11.1.1. Demographic/Medical History

A complete medical history including demography will be collected at the screening visit after informed consent is obtained but before any other procedures are performed. A review of systems will be conducted by the PI or designee to ensure that subjects meet eligibility criteria. Females of childbearing potential will be asked to list their current method(s) of birth control for comparison with the requirements of this study.

11.1.2. Continuous Cardiovascular Monitoring

A DRE Waveline EZ Portable Patient Monitor (Avante Medical Surgical, Louisville KY) will be employed for continuous measurement of 3-lead ECG and vital signs (SpO₂, blood pressure, heart rate, and respiratory rate). Each subject will have the Patient Monitor placed at the bedside, and monitoring will be performed from pre-dose until 24 hours post dose. Subjects may be

monitored for a longer period of time at the discretion of the investigator, based on clinical indication.

- SpO₂ is the saturation of arterial blood with oxygen as measured by pulse oximetry, and reported as a percentage. The SpO₂ sensor will be placed on the index finger of the non-dominant arm using a clip device.
- Blood pressure will be monitored via a standard size-appropriate cuff placed on the non-dominant arm, and measurements will be obtained every 5 minutes until 1 hour post dose, and every 15 minutes thereafter. The frequency of blood pressure sampling may be increased up to every 5 minutes at any time after 1 hour post dose at the discretion of the investigator, based on clinical indication.
- Heart rate and ECG will be obtained using 3 standard chest leads.
- Respiratory rate will be measured by thoracic impedance, via an electrode placed at approximately the right lateral 8th intercostal space.

Note: the measurements obtained during continuous monitoring will not be recorded unless an AE occurs. Safety assessments will be recorded according to the time points below (also refer to [Table 3](#) and [Table 4](#), Study Events Schedules).

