
Continuous cardiovascular monitoring of ECG (3-lead) and vital signs (systolic and diastolic blood pressure (at 5-15 minute intervals), heart rate, respiration rate, and pulse oximetry) will be performed from 1 hour prior to and for 24 hours following Scopolamine HBT or placebo administration. During the first 24 hours and through 48 hours post dose, vital sign monitoring (including body temperature), 12-lead ECG, clinical assessment of neuropsychiatric status (using the BPRS, C-SSRS, and Richmond Agitation and Sedation Scale), and injection site reaction assessments will be performed and documented at specified times. The Digit Symbol Substitution Test will be administered prior to dosing and at 48 hours post dose and Day 8 to detect any persistent cognitive effects. Standard serum chemistry, hematology, and urinalysis testing will be performed at baseline (Day-1), at 24 and 48 hours post dose, and at Day 8. Subjects will be monitored for AEs continuously while in clinic, and AEs will be documented as they are reported. Follow-up for AEs will be conducted via telephone on Days 4 and 30, and via an in-clinic visit on Day 8 unless otherwise reported by the subject. In the event of a potential AE, additional

assessments/testing may be performed if, in the judgment of the investigator or designee, they are warranted for the safety of the subject. AEs will be followed until resolution/stabilization.

Statistical Methods:

Results of safety assessments will be summarized across dosing levels and compared to the placebo group. AEs will be listed by treatment group and body system using MedDRA terms. Confidence intervals for the probability of dose-limiting toxicities and severe adverse events will be estimated based on the number of observed events in each dosing cohort. Scores for injection site assessments, and changes in cognitive and neuropsychiatric scales will be compared for each dosage level relative to placebo. Plasma concentration curves will be fit using noncompartmental analysis to obtain PK parameters for each dosing cohort prior to dosage escalation. PK parameters will be summarized by dosage level, and the parameters C_{max} and AUC_{∞} will be tested statistically for dose proportionality.

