7.6.1.2. Nonextreme Dose-Limiting Toxicities

Nonextreme DLTs are AEs that do not meet the criteria for extreme DLTs but are serious conditions that require immediate medical attention and monitoring. The incidence and severity of these events will be used to determine whether (1) the total cohort size will be increased from 8 to 12 and (2) the need to suspend dosing until the DSMB has completed a safety review and made a recommendation to the sponsor ([Table 6](#)). Nonextreme DLTs include:

- Respiratory
 - Spontaneous respiratory rate < 8 or > 25 breaths per minute, with oxygen saturation less than 90%, which cannot be explained by agitation or other behavioral symptoms and that does not respond immediately to oxygen supplementation via nasal cannula or face mask but for which there is recovery without sequelae prior to the need for intubation
 - Dyspnea at rest
 - Symptomatic bronchospasm
- Neuropsychiatric
 - Neuropsychiatric symptoms (eg, delirium, paranoia, and/or hallucinations) requiring treatment with physostigmine or other medication(s) and, in the opinion of the investigator, responded adequately to treatment
 - Persistent neuropsychiatric symptoms, defined as a score of 4 or higher on any one item or a total score of 40 or higher on the BPRS assessment at the 48-hour, post-dose evaluation
 - Paresthesia that interferes with any activity
 - Athetoid movement
- Cardiac
 - Hypertension, which cannot be explained by agitation or other behavioral symptoms, requiring antihypertensive medication
 - Cardiac arrhythmias or changes that are deemed clinically significant but do not cause the subject to be hemodynamically unstable
 - QTc is > 450 msec for males or > 470 msec for females and has increased > 60 msec from baseline
 - Supraventricular tachycardia alone without hemodynamic compromise
 - Bigeminy or trigeminy not associated with hypotension
- Renal
 - Increase of serum creatinine by ≥ 0.3 mg/dL (≥ 26.4 μ mol/L) or increase to $\geq 150\%$ from baseline or urine output < 0.5 mL/kg/hour for > 6 hours
- Injection Site Reaction

- Any reaction determined to be severe, as defined by the FDA's guidance for injection site reactions ([Appendix B](#)).

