- Regardless of the injection duration, blood sampling for PK analyses will begin with Time 0 at the completion of administration of the injection. Time 0 for the purpose of timing pre-injection procedures and post-dosing data collection is defined as the time the needle is removed at the completion of study drug injection. Both the injection start and end times should be recorded in the source documentation by hours, minutes, and seconds.

Table 7 summarizes treatment groups and dose levels.

Table 7: Treatment Groups and Dose Levels

Cohort	Scopolamine HBT Target Dose (mg/kg)
1	0.005
2	0.007
3	0.011
4	0.014
5	0.021

In addition to continuous cardiovascular monitoring during the 24 hours following administration of study drug, subjects will undergo the following procedures:

- Subjective injection site assessments: a physician, physician assistant, or nurse will ask the subject to rate the intensity of pain, pruritus, tingling, and numbness using the VAS at 5, 10, 15, 30, and 45 minutes and 1, 1.5, 3, 5, 8, and 12 hours after dosing.
- A physician, physician assistant, or nurse will assess the injection site for presence and severity of pain, tenderness, erythema, and induration at 5, 10, 15, 30, and 45 minutes and 1, 1.5, 3, 5, 8, and 12 hours after dosing. This assessment will follow the subjective assessment at each time point.
- 12-lead ECG (supine for at least 5 minutes) will be obtained at 5, 10, 15, 30, and 45 minutes and 1, 1.5, 3, 5, 8, and 12 hours after dosing.
- Vital signs (blood pressure, heart rate, respiration rate, body temperature, and pulse oximetry) will be recorded at 5, 10, 15, 30, and 45 minutes and 1, 1.5, 3, 5, 8, and 12 hours after dosing after the subject has been supine for at least 5 minutes.
- Brief neurological assessment will be performed at 1 hour post dosing (+30 min), after all of the other 1 hour post dosing activities have been completed. Alertness/level of consciousness, orientation, ability to follow commands and coordination will be documented (refer to Section 11.1.5).
- Neuropsychiatric assessments: BPRS will be administered by a psychologist or trained clinician at 6 (+ 2) hours post dose. The + 2 hour window is provided to allow the investigator some discretion should he or she determine the assessment needs to be delayed. The timing may be dependent on the emergence and severity of neuropsychiatric symptoms.

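### Protocol 11.1.2 puts the SpO2 clip and the automatic blood-pressure cuff on the same arm, so the oximeter signal is interrupted or unreliable at each of 104 post-dose cuff cycles to 24 h

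*Protocol*

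**What the plan says.** Protocol section 11.1.2 describes the bedside monitor. The SpO2 "sensor will be placed on the index finger of the non-dominant arm using a clip device". The next item gives a "standard size-appropriate cuff placed on the non-dominant arm". On the timing of the cuff, the same item says that "measurements will be obtained every 5 minutes until 1 hour post dose, and every 15 minutes thereafter". The investigator may return to the 5-minute cycle at any time after the first hour. According to the synopsis, this monitoring "will be performed from 1 hour prior to and for 24 hours following Scopolamine HBT or placebo administration".

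The same section takes respiratory rate from thoracic impedance and says that continuous readings are kept only when there is an adverse event.

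Scheduled vital signs are a separate item. Section 9.1.1.3 reads: "Vital signs (blood pressure, heart rate, respiration rate, body temperature, and pulse oximetry) will be recorded at 5, 10, 15, 30, and 45 minutes", and it continues to 12 hours; section 9.1.2.1 adds 24 hours. Blood pressure and oximetry therefore belong to one set. Section 11.1.3 names neither an arm nor a device for these sets.

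SpO2 enters a DLT in section 7.6.1.2: "Spontaneous respiratory rate < 8 or > 25 breaths per minute, with oxygen saturation less than 90" percent. SAP section 5.1.2 repeats the criterion. SAP section 6.14.3 summarises pulse oximetry descriptively at each scheduled time.

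Neither document puts the two devices on opposite arms, says how to treat an SpO2 value taken during inflation, or describes a monitor function that holds the reading during a cuff cycle.

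**The concern.** A finger oximeter needs an arterial pulse at the finger. A cuff inflated on the same arm stops that pulse, so until it deflates the monitor shows either no value or one that cannot be trusted. Followed as written, section 11.1.2 makes this happen at every cuff cycle.

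Respiratory safety is a live question in this trial. Gasping or labored breathing was seen in the rat studies (section 5.2.2), and saturation below 90% is one element of a nonextreme DLT. Under Table 6, one nonextreme DLT among the first four subjects of a cohort halts dosing. Cuff cycles are also densest in the first hour. The subcutaneous study cited in section 5.2.3/5.2.4 found peak concentration at 10 to 30 minutes; this trial doses intramuscularly, so that timing is only indicative.

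At stake is the quality of the SpO2 readings that staff rely on at the bedside and that would be written down to support an adverse-event or DLT assessment.

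**Working it through.** There is no stated figure to reproduce. The check counts cuff cycles from the stated schedule, sizes the loss under an assumed inflation time, and then reads the DLT criterion element by element.

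**1. Cuff cycles after dosing** (section 11.1.2, cycles counted from dosing)
- 0 to 1 h: 60 / 5 = 12
- 1 to 24 h: 23 × 60 / 15 = 92
- Total: 12 + 92 = 104
- Upper limit if the 5-minute cycle is kept throughout: 1440 / 5 = 288

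**2. Share of time without a valid SpO2.** Inflation time is not in the documents; 20 to 60 s is an assumption. Share = seconds lost per cycle / seconds between cycles.

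| Assumed loss per cycle | First hour (300 s cycle) | Hours 1-24 (900 s cycle) | Total over 24 h |
|---|---|---|---|
| 20 s | 20/300 = 6.7% | 20/900 = 2.2% | 104 × 20/60 = 34.7 min |
| 30 s | 10.0% | 3.3% | 52 min |
| 45 s | 15.0% | 5.0% | 78 min |
| 60 s | 20.0% | 6.7% | 104 min |

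In the first hour this is 12 × 20 s = 4 min up to 12 × 60 s = 12 min.

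**3. Signal left between cycles.** On the 5-minute cycle, 300 − 60 = 240 s to 300 − 20 = 280 s of continuous signal follow each gap.

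**4. Overlap with scheduled vital signs.** The post-dose times to 24 h are 5, 10, 15, 30 and 45 min and 1, 1.5, 3, 5, 8, 12 and 24 h: 12 sets. If cuff cycles are anchored at dosing, all 12 fall on a cycle.

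**5. Can the artefact meet the DLT?** Section 7.6.1.2 requires all of the following:
- Respiratory rate below 8 or above 25. This comes from thoracic impedance, which the cuff does not affect.
- SpO2 below 90%. The cuff could produce this only if the monitor shows a low value rather than none.
- Not explained by agitation or other behavior.
- No immediate response to supplemental oxygen. A cuff artefact ends on deflation.

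The cuff can act on the second element only, so it cannot meet the criterion by itself.

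**The case against.** The strongest case against is that little follows from the shared arm. Several stronger claims are tempting, and the documents do not support them.

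- **A false DLT.** A reader might infer that cuff artefact could trigger one. It cannot do so alone, for the reasons in step 5 of the working. DLTs also go to the investigator, research monitor, pharmacovigilance physician and Data Safety Monitoring Board for review. This part of the objection stands.
- **A missed desaturation.** A reader might infer that a true fall would be overlooked. That is a guess about staff behaviour. At least 4 minutes of signal follow each gap, ECG and impedance respiration continue through it, and a physician is in the treatment room for 4 hours after dosing (section 9.1.1). This also stands.
- **Corrupted recorded data.** Continuous values are kept only with an adverse event, and section 11.1.3 does not tie the scheduled sets to this monitor or arm. SAP section 5.1.5 mentions continuous monitoring and then says that values at the scheduled times are reported, but it names no device either. Listing blood pressure and oximetry in one set does not show that SpO2 is read during inflation; where a blood draw coincides, vital signs may be taken within the preceding 5 minutes. No hypothesis test uses SpO2. The effect on recorded data is therefore conditional.
- **Lost or falsely low.** These are different outcomes. A lost signal yields no value and cannot count as below 90%. The documents do not say which one this monitor gives.

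The objection leaves the placement itself standing. Two adjacent items in one section prescribe devices that interfere with each other, and nothing elsewhere corrects or handles it.

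**Conclusion.** The point holds as a minor measurement defect with a cheap remedy. As written, section 11.1.2 makes SpO2 unavailable or unreliable during each of 104 post-dose cuff cycles to 24 h. The cycle count follows from the documents. The 7-20% and 2-7% shares rest on the assumed 20 to 60 s per cycle and are not documented losses. The loss of signal itself is not stated in the documents; it follows from how a finger oximeter and an upstream cuff work.

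The consequences are avoidable false alarms, short gaps, and doubt about an SpO2 value recorded for an adverse event. If this monitor also supplies the scheduled vital signs, the doubt extends to those values. The finding changes no DLT threshold, escalation rule or statistical test.

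**What to change.** In Protocol section 11.1.2, place the SpO2 clip on the hand opposite the cuff. Add that any SpO2 recorded for scheduled vital signs, adverse-event assessment or DLT assessment is read with the cuff deflated. Leave the DLT thresholds and the monitoring frequency as they are. If there is a reason to keep both devices on one arm, the sponsor should at least state how readings taken during inflation are handled.

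The cost is a change of a few words plus one sentence, with the sponsor and review-board approval that section 15.1.2 requires for any modification. No new equipment is needed. One small downside is that the clip would sit on the dominant hand. Subjects mark four visual analog scale lines and sign the form (Appendix A) at the same post-dose times as the vital signs to 24 h (Table 4), so the clip must be moved briefly or worked around then.
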